APPENDIX B: CLINICAL LABORATORY ANALYTES

Standard Safety Chemistry Panel

Alanine aminotransferase Albumin
Alkaline phosphatase Amylase
Aspartate aminotransferase Bicarbonate
Blood urea nitrogen Calcium

Chloride Creatine kinase

Creatinine Estimated glomerular filtration rate [1]

Gamma-glutamyl transferase Glucose (fasting)

Glycosylated hemoglobin [2] High-sensitivity C-reactive protein

Inorganic phosphorus Lactate dehydrogenase

Lipase Potassium
Sodium Total bilirubin
Total protein Uric acid

- Calculated using the Chronic Kidney Disease Epidemiology Collaboration equation. (Source: CKD-EPI equations for glomerular filtration rate [GFR]. MDCalc. https://www.mdcalc.com/ckd-epi-equations-glomerular-filtration-rate-gfr. Accessed 09 November 2020.)
- Screening Visit only.

Endocrinology

Follicle-stimulating hormone [1]

 Follicle-stimulating hormone test will be performed in women <55 years of age for whom it has been ≥1 year since their last menstrual period.

Hematology

Hematocrit Hemoglobin

Platelets Red blood cell count

White blood cell count and differential [1]

 Manual microscopic review is performed only if white blood cell count and/or differential values are out of reference range.

Pregnancy Test

Urine [1]

1. For women of childbearing potential only.

Lipid Profile

Apolipoprotein B Apolipoprotein E (ApoE)
High-density lipoprotein-ApoE [1] High-density lipoprotein cholesterol
Low-density lipoprotein cholesterol
Triglycerides Very low-density lipoprotein cholesterol

- 1. With and without apolipoprotein C3.
- 2. Calculated using the Friedewald equation unless triglycerides ≥400 mg/dL or low-density lipoprotein cholesterol (LDL-C) ≤50 mg/dL; in both cases, LDL-C level will be measured directly by preparative ultracentrifugation, also referred to as beta quantification. (Source: LDL calculated. MDCalc. https://www.mdcalc.com/ldl-calculated. Accessed 09 November 2020.) In addition, for all patients, LDL-C will be measured by preparative ultracentrifugation, also referred to as beta quantification, at baseline (Visit 2) and at the end of the 8-week Treatment Period (Visit 4).

# **VERSION HISTORY**

| Version | Version Date | Description  |
|---------|--------------|--|
| 1.0     | 20 May 2021  | Original signed version  |
| 2.0     | 07 July 2021 | 3.3.7 Definition of missing date of first dose of study drug, or last dose of study drug; The percent overall study drug compliance 4.2 End of Double-Blind Treatment Analysis 4.3 End of study analysis |

# **LIST OF ABBREVIATIONS**

| Abbreviation | Definition                                     |  |
|--------------|--|--|
| ADaM         | Analysis Data Model Adverse event              |  |
| AE           |  |  |
| ApoB         | Apolipoprotein B                               |  |
| ApoC3        | Apolipoprotein C3 Apolipoprotein E             |  |
| ApoE         |  |  |
| ANCOVA       | Analysis of Covariance                         |  |
| ATC          | Anatomical therapeutic chemical                |  |
| CDISC        | Clinical Data Interchange Standards Consortium |  |
| CETP         | Cholesteryl ester transfer protein             |  |
| CRF          | Case report form                               |  |
| CRO          | Clinical Research Organization                 |  |
| CSR          | Clinical Study Report                          |  |
| ECG          | Electrocardiogram                              |  |
| eCRF         | Electronic case report form                    |  |
| FSH          | Follicle-stimulating hormone                   |  |
| HbA1c        | Glycosylated hemoglobin                        |  |
| HDL          | High-density lipoprotein                       |  |
| HDL-C        | High-density lipoprotein cholesterol           |  |
| ICF          | Informed consent form                          |  |
| IRT          | Interactive response technology                |  |
| ITT          | Intent-to-Treat                                |  |
| LDL          | Low-density lipoprotein                        |  |
| LDL-C        | Low-density lipoprotein cholesterol            |  |
| MedDRA       | Medical Dictionary for Regulatory Activities   |  |
| mITT         | Modified Intent-to-Treat                       |  |
| MMRM         | Mixed model for repeated measures              |  |
| Non-HDL-C    | Non-high-density lipoprotein cholesterol       |  |
| PCSK9        | Proprotein convertase subtilisin kexin type 9  |  |
| PK           | Pharmacokinetics                               |  |
| PP           | Per-Protocol                                   |  |
| PUC          | Preparative ultracentrifugation                |  |
| SAE          | Serious adverse event                          |  |
| SAP          | Statistical Analysis Plan                      |  |
| SDTM         | Study Data Tabulation Model                    |  |
| TEAE         | Treatment-emergent adverse event               |  |
| TESAE        | Treatment-emergent serious adverse event       |  |
| TFLs         | Tables, figures, and listings                  |  |
| TG           | Triglycerides                                  |  |
| VLDL-C       | Very low-density lipoprotein cholesterol       |  |
|              | World Health Organization                      |  |

#### 1 INTRODUCTION

The purpose of this Statistical Analysis Plan (SAP) is to provide a description of the statistical methods to be implemented for the analysis of data from NewAmsterdam Pharma BV Protocol TA-8995-201. The SAP will be finalized prior to database lock. Any deviations from the SAP after database lock will be documented in the final Clinical Study Report (CSR).

#### 2 STUDY OVERVIEW

#### 2.1 Study Objectives

#### 2.1.1 Primary Objective

The primary objective of this study is to evaluate the efficacy of obicetrapib, compared to placebo, at Day 56 in decreasing low-density lipoprotein cholesterol (LDL-C) as an adjunct to high-intensity statin therapy.

#### 2.1.2 Secondary Objectives

The secondary objectives of this study include the following:

- To evaluate the effect of obicetrapib, compared to placebo, at Day 56 on apolipoprotein B
  (ApoB), non-high-density lipoprotein cholesterol (non-HDL-C), and high-density
  lipoprotein cholesterol (HDL-C), as an adjunct to high-intensity statin therapy;
- To assess the mean plasma levels of obicetrapib at steady state on Days 56, 84, 112, and Day 161; and
- To evaluate the safety and tolerability profile of obicetrapib.

#### 2.2 Study Design

#### 2.2.1 Overview

The population for this study includes men and women 18 to 75 years of age, inclusive, with a body mass index <40 kg/m², fasting LDL-C levels >70 mg/dL, and triglyceride levels <400 mg/dL at the Screening Visit, who are currently receiving high-intensity statin therapy.

This study will be a placebo-controlled, double-blind, randomized, Phase 2 dose-finding study to evaluate the efficacy, safety, and tolerability of obicetrapib as an adjunct to high-intensity statin therapy. This study will take place at approximately 20 sites in the United States.

The total duration for the double-blind period for each subject will be up to 25 weeks, including up to 2 weeks for Screening, 8 weeks for blinded study treatment, 4 weeks for safety follow-up, and 11 weeks for PK assessments. Please refer to Table 1 (Schedule of Procedures) below for details.

At the Screening Visit (Visit 1), participants will be required to sign an informed consent form (ICF) before any study-related procedures are performed. After signing the ICF, participants will be assessed for study eligibility.

Up to 2 weeks after the Screening Visit, participants will return to the site on Day 1 (Visit 2) and confirm study eligibility before being randomized and beginning treatment. Approximately 114 eligible participants (38 participants per treatment group) will be randomized in a 1:1:1 ratio to 1 of the following treatment groups:

• 5 mg obicetrapib (one 5 mg obicetrapib tablet + 1 placebo tablet);

- 10 mg obicetrapib (two 5 mg obicetrapib tablets); or
- Placebo (2 placebo tablets).

During the 8-week Treatment Period, the assigned study drugs will be administered by the participants orally and once daily on Day 1 to Day 56. Participants will return to the site every 4 weeks for efficacy, safety, and pharmacokinetic (PK) assessments. Participants, Investigators, the Clinical Research Organization (CRO), and the Sponsor will be blinded to all lipid results from Day 1 (Visit 2) for the first participant through database lock in order to protect blinding to treatment assignment.

Participants will return to the site for a Safety Follow-up Visit (Visit 5) approximately 4 weeks after the end of the Treatment Period for safety and PK assessments.

Participants will return to the site for 2 PK Visits (Visit 6 and 7) approximately 8 and 15 weeks, respectively, after the end of the Treatment Period for safety and PK assessments.

#### Coronavirus Disease 2019 Contingency Measures

In cases of COVID-19 limitations, it is the Investigator's responsibility to assure the safety of participants, including phone or video contact to assess the participant's well-being including any AE, collection of study samples and clinical data as best as possible, and direct shipment of study drug to participant, if necessary. Where available and appropriate, home health care may be considered to facilitate monitoring of safety and study continuity. Documentation of these cases and the site's management of participants should be recorded in the Investigator study files. In the absence of a COVID-19 impact, it is expected that Investigators and participants follow the protocol requirements as set forth.

CONFIDENTIAL

Table 1. Schedule of Procedures

|   | Screening a,b | Tre     | Treatment Period | riod    | Safety Follow-Up | P        | PK       | Early       |
|---|--------------------------|---------|------------------|---------|------------------|----------|----------|-------------|
| Visit   | 1                        | 7       | 3                | 4       | 9                | 9        | 7        | Termination |
| Week  | Up to -2                 | 0       | 4                | 8       | 12               | 16       | 23       | Visit       |
| Day (± Visit Window)  | -14 to -1                | 1       | (∓3)             | 56 (±2) | 84 (±2)          | 112 (±2) | 161 (±2) | Unscheduled |
| Informed consent c                               | X                        |         |                  |         |                  |          |          |             |
| Inclusion/exclusion criteria                                | X                        | $X^{q}$ |                  |         |                  |          |          |             |
| Demographic information                                     | X                        |         |                  |         |                  |          |          |             |
| Medical/surgical history                                    | X                        |         |                  |         |                  |          |          |             |
| Prior/concomitant medications                               | X                        | X       | X                | X       | X                |          |          | X           |
| Weight and height e                              | X                        |         |                  |         |                  |          |          |             |
| Physical examination  | X                        |         |                  | X       |                  |          |          |             |
| Vital signs f                                    | X                        | X       | X                | X       | X                |          |          | X           |
| 12-lead ECG g                                    | X                        |         |                  |         |                  |          |          |             |
| Urine pregnancy test h                           | X                        |         |                  |         |                  |          | X        | X           |
| FSH test i                                       | X                        |         |                  |         |                  |          |          |             |
| Fasting (approximately 10 hours)                            |                          |         |                  |         |                  |          |          |             |
| chemistry and hematology j                       | X                        | X       | X                | X       | X                | X        | X        | X           |
| Fasting (approximately 10 hours) lipid profile k | X                        | X       | X                | X       |                  |          |          | X           |
| PK sample   |                          | X       | X                | ×       | Xm               | ×        | ×        | ×           |
| Randomization   |                          | X       |                  |         |                  |          |          |             |
| Dispense study drug   |                          | X       | X                |         |                  |          |          |             |
| Study drug administration n                      |                          | X       | X                | X       |                  |          |          |             |
| Study drug compliance                                       |                          |         | X                | X       |                  |          |          |             |
| Register visit in IRT                                       | X                        | X       | X                | X       |                  |          |          | X           |
| Adverse events  |                          | X       | X                | X       | X                | X        | X        | X           |
|   |                          | ,       | 1111             | ,       | ' 11 111 11'     | 1        |          |             |

Note: When several assessments are required at the same visit, samples for clinical laboratory assessments should be collected after completing other assessments, such as physical examinations, vital signs, and 12-lead ECGs.

Note: In cases of COVID-19 limitations, it is the Investigator's responsibility to assure the safety of participants, including phone or video contact to assess the participant's well-being including any adverse event, collection of study samples and clinical data as best as possible, and direct shipment of study drug to participant, if necessary. Where available and appropriate, home health care may be considered to facilitate monitoring of safety and study continuity. Documentation of these cases and the site's management of participants should be recorded in the Investigator study files. In the absence of a COVID-19 impact, it is expected that Investigators and participants follow the protocol requirements as set forth.

- If laboratory abnormalities during screening are considered by the Investigator to be transient, then the laboratory tests may be repeated once during screening. The Investigator's rationale for retesting should be documented. If the retest result is no longer exclusionary, the participant may be randomized. ъ.
  - A participant who is screened and does not meet the study eligibility criteria may be considered for rescreening upon Sponsor and/or Medical Monitor consultation and approval. Rescreened participants will be assigned a new participant number. Rescreening should occur no less than 5 days after the last Screening Visit. 6
    - Signed informed consent must be obtained before any study-related procedures are performed.
    - Confirm the participant continues to meet the inclusion and exclusion criteria and assess any updates since the Screening Visit. ن ن

# CONFIDENTIAL NewAmsterdam Pharma BV Protocol TA-8995-201

# Statistical Analysis Plan Version V2.0, 07 July 2021

- Weight and height will be measured at the Screening Visit and will be used to calculate body mass index. Measurement of weight should be performed with the participant dressed in indoor clothing, with shoes removed, and bladder empty. ö
- Vital signs will include body temperature, heart rate, and triplicate blood pressure (systolic and diastolic) measurements. Participants should be in the supine position after at least 10 minutes rest prior to the vital sign measurements. Ŧ.
  - A single, standard 12-lead ECG will be performed by the Investigator or trained site personnel at the Screening Visit and read locally.
    - For women of childbearing potential only.
- FSH test will be performed in women <55 years of age for whom it has been ≥1 year since their last menstrual period.
  - At the Screening Visit only, chemistry panel will include HbA1c. 하는 다. 학생
- addition, for all patients, LDL-C will be measured by preparative ultracentrifugation, also referred to as beta quantification, at baseline (Visit 2) and at the end of the 8-week LDL-C level will be calculated using the Friedewald equation unless TG ≥400 mg/dL or LDL-C ≤50 mg/dL; in both cases, LDL-C level will be measured directly by preparative ultracentrifugation, also referred to as beta quantification. (Source: LDL calculated. MDCalc. https://www.mdcalc.com/ldl-calculated. Accessed 09 November 2020.) In Freatment Period (Visit 4).
- On Day 1, a PK sample will be collected pre-dose. The subsequent post-dose PK samples should be collected once at approximately the same time at each visit.

  PK samples will not be collected during the Safety Follow-up Visit for participants who discontinue study drug early without withdrawing consent or for participants who withdraw prematurely from the study.
  - Two tablets of study drugs will be administered by the participant orally and once daily on Day 1 to Day 56. Study drugs should be administered at approximately the same time each morning, with food. On days with visits scheduled, study drugs should be administered with food following all fasted blood samples. ŋ.

COVID-19 = Coronavirus Disease 2019; ECG = electrocardiogram; FSH = follicle-stimulating hormone; HbA1c = glycosylated hemoglobin; IRT = interactive response technology; LDL-C = low-density lipoprotein cholesterol; PK = pharmacokinetic; TG = triglycerides.

#### 2.2.2 Randomization and Blinding

Participants who meet all eligibility criteria will be randomized into the study. Participants will be randomized in a 1:1:1 ratio to the 5 mg obicetrapib, 10 mg obicetrapib, or placebo treatment groups. At randomization, participants will be stratified according to their Screening Visit (Visit 1) LDL-C level (≥100 or <100 mg/dL). An automated interactive response technology (IRT) system will be used to assign the participant to 1 of the 3 treatment groups.

Participants, Investigators, the CRO, and the Sponsor will be blinded to all lipid results from Day 1 (Visit 2) for the first participant through database lock in order to protect blinding to treatment assignment.

#### 2.2.3 Study Drug

The study drugs used in this study are as follows:

- 5 mg obicetrapib tablet; and
- Matching placebo tablet.

The study drugs listed above will be packaged to provide doses of 5 or 10 mg obicetrapib or placebo only. Participants will be randomized to receive 1 of the 2 doses of obicetrapib or placebo only. Two tablets of study drugs will be administered by the participant orally and once daily on Day 1 to Day 56 at approximately the same time each morning, with food.

Compliance to the study drug regimen will be evaluated by counting unused tablets. Participants will be instructed to bring all unused study drugs to the site at Visits 3 and 4. During the Treatment Period, if compliance is not between 80% and 120%, inclusive, the participant will be counselled about the importance of compliance to the regimen and protocol deviation documented. If the limits are exceeded at 2 consecutive visits, a decision will be made by the Investigator and Sponsor as to whether the participant should be withdrawn from the study.

#### 2.2.4 Sample Size Determination

A sample size of at least 108 evaluable participants (ie, 36 participants per treatment group) will provide >90% power to detect a 30% difference in LDL-C reduction at Day 56 (standard deviation of 15%) for each of the obicetrapib groups compared to the placebo group at a 2-sided significance level of 0.025.

The sample size for this study was determined in order to provide sufficient power for the analyses of the primary efficacy endpoint described above. Therefore, assuming an approximately 5% dropout rate, enrollment of approximately 114 participants (ie, 38 participants per treatment group) is planned for this study. This sample size will also contribute sufficient participant exposure and safety data.

Participants will be stratified according to their Screening Visit (Visit 1) LDL-C levels (≥100 or <100 mg/dL).

### 2.3 Study Endpoints

#### 2.3.1 Primary Efficacy Endpoint

The primary efficacy endpoint is the percent change from Day 1 to Day 56 in LDL-C for each obicetrapib group compared to the placebo group.

#### 2.3.2 Secondary Efficacy Endpoints

The key secondary efficacy endpoints include the following:

- Percent change from Day 1 to Day 56 in ApoB for each obicetrapib group compared to the placebo group;
- Percent change from Day 1 to Day 56 in non-HDL-C for each obicetrapib group compared to the placebo group; and
- Percent change from Day 1 to Day 56 in HDL-C for each obicetrapib group compared to the placebo group.

#### 2.3.3 Safety Endpoints

The safety and tolerability profile of obicetrapib will be assessed by clinical laboratory assessments (chemistry and hematology), vital signs, physical examinations, and the incidence of adverse events (AEs).

#### 3 STATISTICAL METHODOLOGY

#### 3.1 General Considerations

#### 3.1.1 Analysis Day

Analysis day will be calculated from the date of first dose of study drug. The day of the first dose of study drug will be Day 1, and the day immediately before Day 1 will be Day -1. There will be no Day 0.

#### 3.1.3 Definition of Baseline

Unless otherwise stated, Baseline will be defined as the last measurement prior to the first dose of study drug.

#### 3.1.4 Summary Statistics

Categorical data will generally be summarized with counts and percentages of participants. The denominator used for the percentage calculation will be clearly defined. Continuous data will

generally be summarized with descriptive statistics including n (number of non-missing values), mean, median, standard deviation, minimum, and maximum.

#### 3.1.5 Handling of Dropouts and Missing Data

#### Date Values

In cases of incomplete dates (e.g. AE, concomitant medication, and medical history start and/or stop dates), the missing component(s) will be assumed as the most conservative value possible. For example, if the start date is incomplete, the first day of the month will be imputed for the missing day and January will be imputed for the missing month. If a stop date is incomplete, the last day of the month will be imputed for the missing day and December will be imputed for the missing month. Incomplete start and stop dates will be listed as collected without imputation.

Date imputation will only be used for computational purposes such as treatment-emergent status. Actual data values, as they appear in the original CRFs, will be presented within the data listings.

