#### 3.3.7 Study Drug Exposure and Compliance

Participants' exposure to randomized study medication will be summarized with descriptive statistics for the Safety Population. Days of exposure is defined as:

date of last dose of study drug - date of first dose + 1

For those whose date of first dose from the initial blister card dispensed was not available, the date of randomization will be used to assign the date of first dose. For those who failed to provide the date of last dose of study drug, the earliest date between the end of treatment date and the date of end of study/early termination will be used.

A summary will be provided to display counts and percentages of participants in each treatment with exposure in the following categories: <4 weeks, 4 – <8 weeks, and 8+ weeks.

Summary statistics will be presented for percent overall compliance to study medication by treatment and in total. Counts and percentages of participants will also be tabulated by groups with overall compliance < 80%, 80% to 120%, and > 120%.

The percent overall compliance to study medication will be calculated as:

$$100 imes rac{number\ of\ actual\ tablets\ taken}{expected\ tablets\ taken}$$
 ,

Expected tablets taken =  $2 \times$  (the earliest date between the end of treatment date and the date of early termination – the date of randomization +1).

The number of actual tablets taken is the sum of number administered from each blister pack. If number administered from a blister pack is missing, the number administered is considered 16 for the compliance calculation.

A separate listing of derived exposure and compliance will be provided for all randomized participants.

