#### 3.6.1 Adverse Events (AEs)

AEs will be categorized by primary system organ class and preferred term as coded using the MedDRA (version 23.1) category designations. Summaries of AEs, including the count and percentage of participants who experience an AE, will be provided.

An overview of treatment-emergent AEs (TEAEs) will be provided including counts and percentages of participants (and event counts) with the following:

- Any TEAEs overall and by maximum severity
- Any study drug related TEAEs
- Any TEAEs leading to discontinuation of study drug
- Any treatment-emergent serious AEs (TESAEs)
- Any study drug related TESAEs
- Any TEAEs leading to death

Listings will be presented for TEAEs, TESAEs and TEAEs leading to discontinuation of study drug. Counts and percentages of participants will also be presented by system organ class and preferred term for TEAEs, study drug related TEAEs and TESAEs.

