#### 6 PROGRAMMING SPECIFICATIONS

Analyses will be performed using SAS® version 9.4. All available data will be presented in participant data listings which will be sorted by participant and visit date as applicable. Detailed Programming Specifications will be provided in a separate document.

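### The partial-date rule in SAP 3.1.5 has no first-dose floor, so early on-treatment AEs with incomplete start dates can drop out of the TEAE tables

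*SAP*

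**What the plan says.** SAP 3.1.5 (Date Values) applies one imputation rule to AE, concomitant medication and medical history dates. Its stated principle is that "the missing component(s) will be assumed as the most conservative value possible". Its worked rule is that "if the start date is incomplete, the first day of the month will be imputed for the missing day and January will be imputed" where the month is missing. The section then gives the purpose: "Date imputation will only be used for computational purposes such as treatment-emergent status".

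SAP 3.6.1 builds most of its AE displays on treatment-emergent events. The overview (severity, relatedness, discontinuation, serious events, death) and the tables by system organ class and preferred term are limited to TEAEs or TESAEs. For listings it states "Listings will be presented for TEAEs, TESAEs and TEAEs leading to discontinuation of study drug". The List of Abbreviations expands TEAE as "Treatment-emergent adverse event", but no section gives an onset rule.

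Two outputs do not depend on treatment emergence. SAP 3.6.1 also says "Summaries of AEs, including the count and percentage of participants who experience an AE, will be provided", and SAP 6 says "All available data will be presented in participant data listings".

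The SAP's only fallback involving first dose is in 3.3.7, where, if the blister-card date is unavailable, "the date of randomization will be used to assign the date of first dose". That rule serves the exposure calculation and puts no lower bound on AE dates.

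**The concern.** Taking the earliest possible start is cautious for medical history and prior medication. For AE onset it is the opposite, because moving the date back can only push an event out of the treatment-emergent period. The worked rule therefore contradicts the principle stated just before it.

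It also conflicts with how the AEs are collected. Protocol 8.1 documents AEs only from first dose to Visit 7, and sends conditions already present at first dose to medical history unless they change. A recorded AE should therefore be an on-treatment onset or a worsening. Dating it before dosing is nearly always an error, and the error runs towards under-counting.

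What is at stake is the TEAE and TESAE tables and the TEAE listings. With about 38 participants per arm and safety summarised only descriptively, a few events can visibly change a table. The events lost are those that start soon after dosing.

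**Working it through.** The plan gives no figure for this point, so there is nothing to reproduce. The check applies the 3.1.5 rule to the calendar.

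**Inputs.** The rule comes from SAP 3.1.5. Day 1 is the date of first dose (SAP 3.1.1). Treatment runs to Day 56 and AE collection to Visit 7, Day 161 (Protocol 8.1 and Appendix A). Three assumptions are not in the documents: a TEAE has onset on or after first dose; first-dose dates are uniform over a 365-day year; onset days are uniform over the window.

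**Example.** First dose is on the 18th, the AE starts on the 25th and the day is not recorded. The start is imputed as the 1st, 17 days before dosing, and the AE is not counted as treatment-emergent.

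**Day missing.** Let first dose fall on day *d* of a month with *m* days. On-treatment onsets in that month occupy days *d* to *m*, and all are imputed to the 1st. If *d* = 1 none is misdated. If *d* > 1, all *m* − *d* + 1 onset days are misdated. Onsets in later months stay after first dose. Summing over *d* = 2 to *m* gives *m*(*m* − 1)/2 per month:

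- seven 31-day months: 7 × 465 = 3,255
- four 30-day months: 4 × 435 = 1,740
- February: 378
- total 5,373; 5,373 / 365 = 14.72 onset days per participant on average. The range is 0 (dosing on the 1st) to 30 (dosing on the 2nd of a 31-day month).

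For a 28-day window each count is capped at 28, so the total is 7 × 462 + 4 × 434 + 378 = 5,348, or 14.65 days.

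| Onset window | Mean share of day-missing AEs misdated | Range |
|---|---|---|
| 28 days | 14.65 / 28 = 52.3% | 0-100% |
| 56 days | 14.72 / 56 = 26.3% | 0 to 30/56 = 53.6% |
| 161 days | 14.72 / 161 = 9.1% | 0 to 30/161 = 18.6% |

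Of on-treatment onset days in the first-dose month itself, 5,373 / 5,738 = 94% are misdated. The denominator is the sum of *m*(*m* + 1)/2: 7 × 496 + 4 × 465 + 406.

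**Share of all AEs.** With an assumed 1-5% of AEs lacking a day:

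- 56 days: 26.3% × 1% to 26.3% × 5% = 0.26-1.31%
- 161 days: 9.1% × 1% to 9.1% × 5% = 0.09-0.46%

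**Month missing.** The start becomes 1 January. An onset in the calendar year of first dose is misdated unless dosing began on 1 January. For first dose on day *n* ≥ 2 of the year, the affected onset days number the smaller of *L* and 366 − *n*. Summed over *n*, this is *L*(*L* + 1)/2 + *L*(364 − *L*).

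- *L* = 56: (1,596 + 17,248) / (365 × 56) = 18,844 / 20,440 = 92%
- *L* = 161: (13,041 + 32,683) / (365 × 161) = 45,724 / 58,765 = 78%

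24 July is day 205 of the year, and 205 + 160 = 365. It is therefore the last first-dose date that keeps Day 161 in the same year. For first dose from 2 January to 24 July, every on-study AE with a missing month is misdated.

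**With a first-dose floor.** If the imputed start is the later of the 3.1.5 date and first dose, no on-treatment AE in the first-dose month is dated before dosing: 0 in the full enumeration.

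**The case against.** The strongest reply is that the loss depends on a TEAE definition the SAP does not contain. Since Protocol 8.1 collects AEs only from first dose, a flag based on collection or worsening would lose nothing. That is correct, and the missing definition is a gap in its own right. But 3.1.5 says imputed dates are used for treatment-emergent status, so the SAP intends a date comparison. Under the ordinary meaning of TEAE, the written rule gives the wrong answer.

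Several points about size stand:

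- AEs are collected to Day 161, so the 9% figure matches the whole collection period. The 26% and 52% figures apply to shorter windows.
- Missing days may be commoner between Day 112 and Day 161, the longest gap between visits, where a missing day cannot put the AE before first dose.
- Data queries (Protocol 10.1.5) should keep partial dates few, and 24-hour SAE reporting with follow-up (Protocol 8.3) makes an SAE with an unknown onset day unusual.
- A missing month is likely rare.
- No hypothesis test is affected.
- The named safety endpoint is the incidence of AEs, and the general AE summary and the data listings keep every event.

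Two further replies carry less weight. The 1st/January rule is introduced as an example, but it is the only operative instruction and a programmer would follow it. The separate programming specifications might add a floor; they are not among these documents. Version 2.0 of the SAP placed its rule for missing dose dates in the SAP itself, so this rule belongs there too.

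**Conclusion.** The concern holds. As written, 3.1.5 can date on-treatment AEs before first dose and so remove them from the TEAE and TESAE displays, contrary to its own conservative principle and to the AE collection rule in Protocol 8.1.

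The effect is probably small and similar across arms. Over the full 161 days about 9% of day-missing AEs are affected, which is 0.1-0.5% of all AEs if 1-5% lack a day. Over 56 days the figures are 26% and 0.3-1.3%. These results rest on the assumed TEAE definition, uniform first-dose dates and onset, and the assumed rate of missing days.

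The point still merits a change. The loss is concentrated in early-onset events, and every AE breakdown that 3.6.1 itemises is restricted to TEAEs or TESAEs, which makes them the main tolerability display. Confidence is medium, because the number of partial dates and the content of the programming specifications are unknown.

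**What to change.** In SAP 3.1.5, add for AE start dates only:

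> If the known date parts allow onset on or after first dose, and the stop date (imputed if incomplete) is not before first dose, impute the later of the first-dose date and the earliest date the known parts allow. The event is treatment-emergent unless the known parts or the stop date show that it began before first dose.

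In SAP 3.6.1, add:

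> A TEAE is an AE with onset or worsening on or after the first dose of study drug.

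State that this definition governs worsening of a condition that began before dosing. Take the first-dose date from 3.3.7, including its fallback to randomization. Leave the existing rule in place for medical history and medications.

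The cost is three sentences, a brief cross-reference and a small programming change, with no new data. TEAE counts may rise slightly, and an occasional pre-dose event with a partial date may be counted as treatment-emergent. That error is in the cautious direction.
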